The Pharmacodynamic (PD) Analysis Set will be the group of subjects who have both baseline and at least 1 postbaseline assessment of at least 1 PD parameter.

Primary Safety and Efficacy and Key Secondary Analyses (revised per Amendment 02)

The primary endpoints, MACE, and MACE+, will be analyzed using a Cox proportional hazards model that includes factors for treatment and stratification variable (presence of established CV disease or CV risk factors without established CV disease). (revised per Amendment 02) For secondary and exploratory endpoints a 2-sided $\alpha = 0.05$ significance level will be used. The MACE analysis (“interim” analysis) will be conducted when

460 adjudicated MACE events have been recorded; the other analyses will be conducted when 1401 adjudicated MACE+ events have been recorded, and the study has completed. (revised per Amendment 02)

Sequential Gatekeeping Testing Procedure

The following closed sequential gatekeeping testing procedure (SGTP) will be used to control the family-wise error rate (FWER) at $\alpha = 0.05$ (2-sided) in testing the 2 primary endpoints (MACE and MACE+) and 1 key secondary endpoint, conversion to T2DM. (revised per Amendment 02)

Let H_{01} be the gatekeeping null hypothesis for noninferiority testing of the MACE endpoint using a noninferiority margin of 1.4.

[figure not shown]
Let H_{02} and H_{03} be the null hypotheses for superiority testing: MACE+ and conversion to T2DM, respectively. (revised per Amendment 02)

The SGTP testing hierarchy is presented below. (revised per Amendment 02)

- STEP1: At the interim analysis, test the noninferiority hypothesis for MACE, H_{01} ($\alpha = 0.025$, 1-sided). If H_{01} is rejected, then proceed to STEP2, otherwise stop testing and the trial will be stopped.
- STEP2: At study completion the hypothesis H_{02} ($\alpha = 0.05$, 2-sided) is tested first. If the hypothesis is rejected, then proceed to test H_{03} ($\alpha = 0.05$, 2-sided). If H_{02} is not rejected, then testing stops at this point.

The flowchart below presents the SGTP:

Flowchart for the Sequential Gatekeeping Testing Procedure

Primary Endpoint Analyses

- **Time to MACE:** The estimate of the hazard ratio of lorcaserin HCl to placebo and the corresponding 1-sided 97.5% confidence interval (CI) will be calculated. Noninferiority of lorcaserin HCl to placebo will be declared if the upper limit of the 97.5% CI is less than the noninferiority margin of 1.4. The Total Time Analysis Set will be used as the primary analysis at the interim analysis. (revised per Amendment 02) The On-Treatment Analysis Set and the On-Treatment plus 30 Days Analysis Set will be used as sensitivity analyses at study completion. (revised per Amendment 02)

- **Time to MACE+:** The estimate of the hazard ratio of lorcaserin HCl to placebo and the corresponding 2-sided 95% CI will be calculated. The Total Time Analysis Set will be used as the primary analysis. (revised per Amendment 02) The On-Treatment Analysis and the On-Treatment plus 30 Days Analysis Set will be used as sensitivity analyses.

The incidence rate difference and the incidence rate ratio between lorcaserin HCl and placebo will also be analyzed as supportive analysis for the primary endpoints above, at study completion. (revised per Amendment 02)

Sensitivity analyses will be performed at study completion for the MACE and MACE+ endpoints using the Total Time Analysis Set. (revised per Amendment 02) This sensitivity analysis will not count a MACE or MACE+ event that occurs after the subject starts another weight reduction medication or undergoes bariatric surgery. (revised per Amendment 02)

Key Secondary Endpoint Analysis (revised per Amendment 02)

- **Time to conversion to T2DM:** The estimate of the hazard ratio of lorcaserin HCl to placebo and the corresponding 2-sided 95% CI will be calculated. The Prediabetes and Total Time Analyses Sets will be used as the primary for this analysis. The Prediabetes along with the On-Treatment Analysis Set and the On-Treatment plus 30 Days Analysis Set will be used as a sensitivity analysis at study completion. (revised per Amendment 02)

Secondary Endpoint Analyses

For the following endpoints, a Cox proportional hazards model with factors for treatment and stratification variable (presence of established CV disease or CV risk factors without established CV disease) will be used. The estimate of the hazard ratio of lorcaserin HCl to placebo and the corresponding 2-sided 95% CI will be calculated.

- The time-to-event of each component of MACE+. The Total Time Analysis Set will be used as the primary analysis. The On-Treatment Analysis Set and the On-Treatment plus 30 Days Analysis Set will be used as sensitivity analyses.
- Time-to-event of all-cause mortality. The Total Time Analysis Set will be used as the primary analysis. The On-Treatment Analysis Set and the On-Treatment plus 30 Days Analysis Set will be used as sensitivity analyses.
- Time-to-event of new onset renal impairment or worsening existing renal impairment in all subjects. The ITT Analysis Set will be used for this analysis. (revised per Amendment 02)
- Time-to-event of new onset renal impairment or worsening existing renal impairment in subjects with T2DM at Baseline. The T2DM Analysis Set will be used for this analysis.
- Time-to-event of new onset renal impairment or worsening existing renal impairment in subjects with prediabetes at Baseline. The Prediabetes Analysis Set will be used for this analysis. (revised per Amendment 01)
- Time-to-event of improvement in renal function. The T2DM Analysis Set will be used for this analysis.
- Time-to conversion to T2DM in subjects without any type of diabetes at Baseline. The Nondiabetes Analysis Set will be used for this analysis. (revised per Amendment 01)
- Time to conversion to normal glucose homeostasis ($HbA_{1c} \leq 5.6\%$ and fasting plasma glucose < 100 mg/dL without any antidiabetic treatment). The Prediabetes Analysis Set will be used for this analysis. (revised per Amendments 01 and 02)
- Change from Baseline in HbA_{1c} at 6 months in subjects with T2DM at Baseline will be analyzed using an analysis of covariance (ANCOVA) model with treatment and stratification variable (presence of established CV disease or CV risk factors without established CV disease) as factors, and baseline HbA_{1c} , as a covariate. Comparison between lorcaserin HCl and placebo will be made at 6 months. The estimated treatment difference between lorcaserin HCl and placebo and the 2-sided 95% CI will be calculated. The

T2DM Analysis Set will be used for this analysis. (revised per Amendment 01)

- The proportion of subjects who meet FDA-defined valvulopathy in echocardiographically determined heart valve changes will be analyzed using logistic regression including treatment as a factor and baseline BMI as a covariate. Comparison between lorcaserin HCl and placebo will be made at 1 year. The FDA-defined Valvulopathy Analysis Set will be used for this analysis.
- The proportion of subjects with FDA-defined valvulopathy at Baseline who demonstrate worsened FDA-defined valvulopathy at 1 year will be analyzed using logistic regression including treatment as a factor and baseline BMI as a covariate. A comparison between lorcaserin HCl and placebo will be made at 1 year. The ITT analysis set in subjects with FDA-defined valvulopathy at Baseline will be used for this analysis. (revised per Amendment 01)
- The change from Baseline in echocardiographically-determined pulmonary arterial systolic pressure will be analyzed using a mixed-effects model with repeated measures with treatment as a factor and baseline BMI as a covariate. Comparison between lorcaserin HCl and placebo will be made at 1 year and the corresponding 2-sided 95% CI will be calculated. The ITT will be used for this analysis. (revised per Amendment 01)

Exploratory Endpoint Analyses

- The change from Baseline in CV risk factors (body weight, BMI, waist and hip circumference, dyslipidemia, insulin level, hypertension, inflammatory biomarkers) will be analyzed using a mixed-effects model with repeated measures with treatment and stratification variable (presence of established CV disease or CV risk factors without established CV disease) as factors. Comparison between lorcaserin HCl and placebo will be made at 1 year. The ITT will be used for this analysis.
- For subjects with NAFLD at Baseline, the change from Baseline in LFTs (AST, ALT, alkaline phosphatase, GGT, total and direct bilirubin) will be analyzed using a mixed-effects model with repeated measures with treatment and stratification variable (presence of established CV disease or CV risk factors without established CV disease) as factors. Comparison between lorcaserin HCl and placebo will be made at 1 year. The ITT will be used for this analysis.
- The proportion of subjects who meet FDA-defined valvulopathy in echocardiographically determined heart valve changes will be analyzed using logistic regression including treatment as a factor and baseline BMI as a covariate. Comparison between lorcaserin HCl and placebo will be made at 2 years and yearly thereafter. The FDA-defined Valvulopathy Analysis Set will be used for this analysis.
- The change from baseline in eGFR and ACR will be analyzed using a mixed-effects model with repeated measures with treatment as a factor and baseline value as a covariate. Comparison of the trajectories for lorcaserin HCl and placebo will be made at 1 year, yearly thereafter, and at EOS. The ITT will be used for this analysis.
- The change from Baseline in echocardiographically-determined pulmonary arterial systolic pressure will be analyzed using a mixed-effects model with repeated measures with treatment as a factor and baseline BMI as a covariate. Comparison between lorcaserin HCl and placebo will be made at 2 years and yearly thereafter. The ITT will be used for this analysis.
- Change from Baseline in HbA_{1c}, FPG, fasting insulin levels, and HOMA-IR at 6 months in subjects with T2DM at Baseline will be analyzed using an ANCOVA model with treatment and stratification variable (presence of established CV disease or CV risk factors without established CV disease) as factors, and baseline HbA_{1c}, as a covariate. Comparison between lorcaserin HCl and placebo will be made at 6 months. The estimated treatment difference between lorcaserin HCl and placebo and the 2-sided 95% CI will be calculated. The T2DM Analysis Set will be used for this analysis, in the following subpopulations. (revised per Amendments 01 and 02)

- Subjects with (HbA_{1c}>7%) at Baseline
 - Subjects who have not been treated with antidiabetic agents at Baseline
 - Subjects who are on monotherapy with oral antidiabetic agents at Baseline.
 - Subjects with early T2DM (duration of diagnosis of diabetes is less than 5 years) at Baseline.
- Proportion of subjects with reduction in the number of OAD medications or reduction in the dosage of OAD medications in the following subpopulations of subjects with T2DM at Baseline will be analyzed using logistic regression including treatment as factor. Comparison between lorcaserin HCl and placebo will be made at 6 months. The T2DM Analysis Set will be used for this analysis, in the following subpopulations: (revised per Amendment 01)
 - Subjects with (HbA_{1c}>7%) at Baseline
 - Subjects who are on monotherapy with oral antidiabetic agent at Baseline
 - Subjects with early T2DM (duration of diagnosis of diabetes is less than 5 years) at Baseline.
 - Proportions of subjects with at least a 1-stage reduction in an obesity-related complication (prediabetes, metabolic syndrome, T2DM, hypertension, and hypertriglyceridemia/dyslipidemia), incidence of other obesity-related complications will be collected through AE reports, medical history, and use of concomitant medications, will be analyzed using logistic regression including treatment as factor. Comparison between lorcaserin HCl and placebo will be made at 1 year and EOS. The Safety Analysis Set will be used for this analysis. (revised per Amendment 01)

Logistic regression including treatment as factor will be used for the following endpoints. Comparison between lorcaserin HCl and placebo will be made at EOS. (revised per Amendment 01)

The Prediabetes Analysis Set will be used for the following analyses: (revised per Amendment 01)

- Proportions of subjects with prediabetes at Baseline who develop new diagnosis of diabetic retinopathy at EOS (revised per Amendment 01)
- Proportions of subjects with prediabetes at Baseline who develop new diagnosis of diabetic neuropathy at EOS (revised per Amendment 01)

The T2DM Analysis Set will be used for the following analyses: (revised per Amendment 01)

- Proportions of subjects with T2DM at Baseline who develop new diagnosis of diabetic retinopathy at EOS (revised per Amendment 01)
- Proportions of subjects with T2DM at Baseline who develop new diagnosis of diabetic neuropathy at EOS (revised per Amendment 01)

Pharmacokinetic Analyses

Not applicable

Pharmacodynamic Analyses

A PD analysis plan may be defined and reported separately.

Biomarker Analyses

A biomarker analysis plan may be defined and reported separately.

Pharmacogenomic Analyses

A pharmacogenomic analysis plan may be defined and reported separately.

Safety Analyses

Evaluations of safety will be performed on the Safety Analysis Set. The incidence of AEs (including changes from baseline in physical examination), out-of-normal-range laboratory safety test variables, abnormal ECG findings, along with change from Baseline in laboratory safety test variables, ECGs, suicidality and vital sign measurements will be summarized yearly by treatment group using descriptive statistics.

The incidence of AEs of interest will be summarized separately. In addition, for each AE of interest, Kaplan-Meier curves and median time and 95%CI will be presented. The Safety Analysis Set will be used for this analysis.

Other Analyses

- Not applicable

Interim Analysis

There will be 1 interim analysis; when 460 adjudicated MACE events have occurred, the primary analysis for MACE will be conducted. This will be the analysis to rule out a hazard ratio of 1.4. The study will continue to accrue events until the required number of MACE+ have occurred. (revised per Amendment 02) Sensitivity analysis for MACE endpoint will be performed after all the MACE+ events have accrued. (revised per Amendment 02) At the time of MACE+ analyses, there will be approximately 600 MACE events.

The interim analysis for MACE endpoint will be performed by an independent statistician and governed by an independent DMC and is anticipated to occur on or before (approximately) Jul 2017. (revised per Amendment 02) The interim analysis will be conducted to establish whether the MACE primary objective has been achieved. To maintain the integrity and credibility of the trial, procedures will be implemented to ensure the DMC and independent statistician have sole access to evolving information from the clinical trial regarding comparative efficacy and safety data aggregated by treatment group. Full details of the DMC procedures including primary responsibilities of the DMC, its relationship with other trial components, its membership, and the purpose and timing of its meetings will be documented in the DMC Charter. These details will also include procedures to ensure confidentiality and proper communication (as outlined in the Study Integrity Charter), the safety and statistical monitoring guidelines to be implemented by the DMC, and an outline of the content of the closed reports and open reports that will be provided to the DMC. (revised per Amendment 02)

At the interim analysis for MACE, the estimate of the hazard ratio of lorcaserin HCl to placebo and the corresponding 97.5% CI will be calculated. Noninferiority between lorcaserin HCl and placebo will be declared if the upper limit of the 97.5% CI is less than or equal to the noninferiority margin of 1.4. If the upper limit of the 97.5% CI is greater than 1.4, then lorcaserin HCl will be declared as not noninferior to placebo and the trial will stop.

If noninferiority between lorcaserin HCl and placebo is confirmed when 460 adjudicated MACE events are observed at approximately 43 months from the start of the study, then the study will be continued to observe 1401 MACE+ events at approximately 54 months from the start of the study, and a minimum median treatment duration of 2.5 years have accrued. (revised per Amendment 02) The events for MACE+ and T2DM will be tested according to the SGTP described previously, upon study completion. (revised per Amendment 02)

Sample Size Rationale

A sample size of 12,000 subjects should provide the required power for the primary endpoints and key secondary endpoint as follows:

Primary Endpoints (revised per Amendment 02)

- For 460 MACE events to have occurred by approximately 43 months from start of the study, providing 95% power to exclude a noninferiority margin of 1.4, assuming an annual background rate of 1.5%, 15-month accrual period, 5% annual drop-out rate, $\alpha = 0.025$, and a 1-sided test
- For 1401 MACE+ events to have occurred by approximately 54 months from the start of the study, providing >85% power to detect a 15% risk reduction with lorcaserin HCl, assuming an annual background

rate of 3.5%, 15-month accrual period, 5% annual drop-out rate, $\alpha = 0.05$, and a 2-sided test

Key Secondary Endpoint (revised per Amendment 02)

- For 457 events of conversion to T2DM in subjects who are prediabetic at the time of enrollment (~33%) to have occurred by approximately 54 months from the start of the study, providing 86% power to detect a 25% risk reduction with lorcaserin HCl, assuming an annual background rate of 4%, 15-month accrual period, 5% annual drop-out rate, $\alpha = 0.05$ and a 2-sided test.

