 - Subjects who are on monotherapy with oral antidiabetic agent at Baseline
 - Subjects with early T2DM (duration of diagnosis of diabetes is less than 5 years) at Baseline.
- Proportions of subjects with prediabetes at Baseline who develop new diagnosis of diabetic retinopathy or new diagnosis of diabetic neuropathy by EOS (revised per Amendment 01)
- Proportions of subjects with T2DM at Baseline who develop new diagnosis of diabetic retinopathy or new diagnosis of diabetic neuropathy by EOS (revised per Amendment 01)

Analysis Sets

The Safety Analysis Set will be the group of subjects who received at least 1 dose of study drug and had at least 1 postdose safety assessment.

The Intent-to-Treat set (ITT) will be the group of all randomized subjects regardless of whether they took study drug or not.

- Total Time Analysis Set: Using the ITT, events are counted that occur while subjects are on and off treatment. Subjects with no events who discontinue early or complete the study will be censored at their last study contact (see details in the SAP). This will be used for the primary analysis.
- On-Treatment plus 30 Days Analysis Set: Using the ITT, events are counted that occur while subjects are on treatment and up to 30 days from their last dose. Subjects with no events who discontinue early or complete the study will be censored at their last dose day plus 30 days.
- On-Treatment Analysis Set: Using the ITT, events are counted that occur while subjects are on treatment. Subjects with no events who discontinue early or complete the study will be censored at their last dose day.
- Prediabetes Analysis Set: This set includes all subjects in the ITT set without a history of any type of diabetes and who are prediabetic at Baseline. Definition of prediabetes will be found in the SAP. (revised per Amendment 01)
- Nondiabetes Analysis Set: This set includes all subjects in the ITT set without a history of any type of diabetes at Baseline. Definition of nondiabetes will be found in the SAP. (revised per Amendment 01)

T2DM Analysis Set: This set will be all subjects in the ITT who have T2DM at Baseline.

FDA-defined Valvulopathy Analysis Set: This set will be all subjects in the ITT without FDA-defined valvulopathy at Baseline. The data from this study will be pooled with the data from the 3 pivotal lorcaserin HCl studies (APD356-009, -010, and -011).

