9.5.1.3 Primary Safety/Efficacy Assessments

MACE/MACE+ EVENTS

Potential MACE/MACE+ events will be recorded throughout the study.

During this study, the endpoints of MACE and MACE+ will need to be reported in an expedited fashion by investigators to the Clinical Endpoint Committee (CEC) and to the Eisai Product Safety Department. MACE/MACE+ events will be recorded on the Adverse Event (AE) case report form, but these events will not be considered as AEs, nor will they be recorded as serious adverse events (SAEs) in the clinical trial database or be required to be reported to regulatory authorities in an expedited timeframe, with the exception of MACE or MACE+ events that are considered by the investigator to be at least possibly related to the study drug (ie, where there is evidence to suggest a causal relationship). (revised per Amendment 01)

Details of which events to report, how to report, and the required supporting documentation will be detailed in a separate manual provided to the sites.

In order to reduce intra- and intersite variability, the CEC will centrally review each potential MACE and MACE+ event to ensure standardization of data collection and interpretation of such events reported throughout the study. The CEC will determine whether each potential event meets criteria for MACE or MACE+. The CEC will remain blinded to treatment allocation and its activities and the criteria for classification of MACE/MACE+ events will be documented in the CEC Charter.

CONVERSION TO DIABETES

HbA_{1c} and FPG will be measured in blood samples collected at Screening, Baseline, and specified timepoints throughout the study.

HbA_{1c}, FPG and when available, additional components of the ADA diagnostic criteria will be assessed. All potential cases of conversion to diabetes will undergo central review of relevant supporting data. (revised per Amendment 01)

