9.5.1.5 Safety Assessments

Safety assessments will consist of monitoring and recording all AEs and SAEs; regular monitoring of hematology, blood chemistry, and urinalysis; periodic measurement of vital signs and electrocardiograms (ECGs); and performance of physical examinations. Additional safety assessments specific to this study will include echocardiography.

AES AND EVENTS ASSOCIATED WITH SPECIAL SITUATIONS (revised per Amendment 01)

An adverse event (AE) is any untoward medical occurrence in a subject or clinical investigation subject administered an investigational product. An AE does not necessarily have a causal relationship with the medicinal product. For this study, the study drug is lorcaserin HCl.

The criteria for identifying AEs are:

- Any unfavorable and unintended sign (including an abnormal laboratory finding), symptom, or disease temporally associated with the use of an investigational product, whether or not considered related to the investigational product
- Any new disease or exacerbation of an existing disease
- Any deterioration in nonprotocol-required measurements of a laboratory value or other clinical test (eg, ECG or x-ray) that results in symptoms, a change in treatment, or discontinuation of study drug
- Recurrence of an intermittent medical condition (eg, headache) not present pretreatment (Baseline)
- An abnormal laboratory test result should be considered an AE if the identified laboratory abnormality leads to any type of intervention, whether prescribed in the protocol or not.

A laboratory result should be considered by the investigator to be an AE if it:

- Results in the withdrawal of study drug
- Results in withholding of study drug pending some investigational outcome
- Results in an intervention, based on medical evaluation (eg, potassium supplement for hypokalemia)
- Results in any out-of-range laboratory value (Sponsor's Grading for Laboratory Value provided as reference in [Appendix 3](#)) that in the investigator's judgment fulfills the definitions of an AE with regard to the subject's medical profile (revised per Amendment 01)

All AEs observed during the study will be reported on the CRF. All AEs, regardless of relationship to study drug or procedure, should be collected beginning from the time the subject signs the study ICF through the end of the study. –(revised per Amendment 01)

MACE and MACE+ events and other study-specific AEs of interest will be followed until EOS. (revised per Amendment 01)

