## 5.2 STUDY SUBJECTS

#### **5.2.1** Definitions of Analysis Sets

The number (percent) of subjects included in each analysis set will be presented by analysis set, treatment group and overall. The description of the analysis data sets are:

- The Safety Analysis Set: will be the group of subjects who received at least one dose of study drug and had at least one post dose safety assessment.
- The Intent-to-Treat (ITT) Set: will be the group of all randomized subjects regardless of whether they took study drug or not. This is the same as the Full Analysis Set.
- Total Time Analysis Set: Using the ITT, events are counted that occur while subjects are on and off treatment. Subjects with no events will be censored at their last study contact or at the visit following Sponsor Notification of Study Completion, whichever

- occurs first. This analysis set will be used for the primary analysis. See Section 8.5 for censoring algorithm.
- On-Treatment plus 30 Days Analysis Set: Using the ITT, events are counted that occur
  while subjects are "on treatment" and up to 30 days from their last dose. Subjects with
  no events who discontinue early or complete the study will be censored at their last dose
  date plus 30 days. See Section 8 for definition of "on treatment" and Section 8.5 for
  censoring algorithm.
- On-Treatment Analysis Set: Using the ITT, events are counted that occur while subjects are "on treatment". Subjects with no events who discontinue early or complete the study will be censored at their last dose date. See Section 8 for definition of "on treatment" and Section 8.5 for censoring algorithm.
- Prediabetes Analysis Set: This set includes all subjects in the ITT set without a history of any type of diabetes and who are prediabetic at Baseline (defined in Section 8).
- Nondiabetes Analysis Set: This set includes all subjects in the ITT set without a history of any type of diabetes at Baseline (defined in Section 8).
- T2DM Analysis Set: This set will be all subjects in the ITT who have T2DM at Baseline (defined in Section 8).
- FDA-defined Valvulopathy Analysis Set: This set will be all subjects in the ITT without FDA- defined valvulopathy at Baseline (defined in Section 8.4). The data from the ECHO sub-study will be pooled with the ECHO data from the 3 pivotal lorcaserin HCl studies (APD356-009, APD356-010, and APD356-011).

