#### 5.6 SAFETY ANALYSES

All safety analyses will be performed on the Safety Analysis Set. The incidence of AEs (including changes from baseline in physical examination), out-of-normal-range laboratory safety test variables, abnormal ECG findings, along with change from Baseline in laboratory safety test variables, ECGs, and vital sign measurements summarized yearly by treatment group using descriptive statistics.

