#### **5.6.2** Adverse Events

The AE verbatim descriptions (investigator terms from the CRF) will be classified into standardized medical terminology using the Medical Dictionary for Regulatory Activities (MedDRA - Version 16.0 or higher). AEs will be coded to the MedDRA lower level term (LLT) closest to the verbatim term. The linked MedDRA preferred term (PT) and primary system organ class (SOC) are also captured in the database.

All AEs observed during the study will be reported on the CRF. All AEs, regardless of relationship to study drug or procedure, should be collected beginning from the time the subject signs the study ICF through the end of the study and for a minimum of 30 days after the last dose. Serious AEs will be collected through the end of study, and for a minimum of 30 days after the last dose.

A treatment-emergent AE (TEAE) is defined as an AE that emerges during treatment, having been absent at pretreatment (Baseline) or

- Reemerges during treatment, having been present at pretreatment (Baseline) but stopped before treatment, or
- Worsens in severity during treatment relative to the pretreatment state, when the AE is continuous.

Only those AEs that were treatment emergent (including CEC adjudicated events) will be included in summary tables. All AEs, treatment emergent or otherwise, will be presented in subject data listings.

TEAEs will be summarized by treatment group on the Safety Analysis Set. The incidence of TEAEs will be reported as the number (percentage) of subjects with TEAEs by SOC and PT (these summaries will be done with and without CEC adjudicated events). A subject will be counted only once within a SOC and PT, even if the subject experienced more than one TEAE within a specific SOC and PT. The number (percentage) of subjects with TEAEs will also be summarized by maximum severity (mild, moderate, or severe). The number (percentage) of subjects with TEAEs will also be summarized by relationship to study drug (Yes = related, and No = Not related).

AEs will be summarized by the following subgroups: age (< 65 years,  $\geq$  65 years to <75 years,  $\geq$ 75 years), sex (male, female), race (white, black, other), presence of established CV disease or CV risk factors without established CV disease, pre-diabetes at Baseline, and T2DM at Baseline (with and without).

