#### **8.6 DEFINITION OF VISIT WINDOWS**

Table 4 of the protocol presents the schedule of procedures/Assessments. Some procedures/assessments are performed at 3 months, 6 months or yearly intervals. Table 8 presents the protocol specified visits/months and corresponding time windows used for visit-wise analyses are presented in terms of days relative to the first dose. For subjects that are randomized, the last available assessment on or before the randomization date will be used as the Baseline-Day 1. If more than one measurement is included in a visit window, the measurement collected closest to the scheduled date will be used in the analysis. In the case where two measurements were collected an equal number of days before and after the Scheduled Day the later of the two measurements will be used for analysis.

For ECHO and PAH assessments when assessing a new or worsened event then the most severe assessment will be selected if 2 or more assessments fall within a visit window.

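### The Safety Analysis Set drops dosed subjects with no postdose safety record and leaves membership unclear for a subject whose only postdose record is an early endpoint event

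*Protocol*

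**What the plan says.** The protocol defines the Safety Analysis Set twice, in the Synopsis (Analysis Sets) and in 9.7.1.2, as subjects "who received at least 1 dose of study drug and had at least 1 postdose safety assessment". SAP 5.2.1 uses the same two conditions: subjects who "received at least one dose of study drug and had at least one post dose safety assessment". Neither document says which record satisfies the second condition.

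SAP 5.6 states: "All safety analyses will be performed on the Safety Analysis Set". That covers exposure, AEs (including those leading to death), laboratory values, vital signs and ECGs. SAP 5.2.6 (prior and concomitant therapy) and 5.2.7 (compliance) use the same set.

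On endpoint events the documents pull in two directions. Protocol 9.5.1.3 says of MACE and MACE+ that "these events will not be considered as AEs, nor will they be recorded as serious adverse events (SAEs) in the clinical trial database", with an exception for events judged at least possibly related to study drug. The same sentence has them entered on the AE case report form. SAP 5.6.2 says: "Only those AEs that were treatment emergent (including CEC adjudicated events) will be included in summary tables". It also asks for the SOC and preferred-term summaries with and without those events.

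**The concern.** The second condition makes membership depend on what happens after dosing. Table 4 of the protocol gives the first dose at Visit 2 and the next scheduled visit at Month 3. A subject who takes drug and is never heard from again is therefore excluded by a stated rule. Such subjects probably have short exposure, so leaving them out tilts the exposure summary upward, and early loss could differ between arms.

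The second problem is ambiguity. Take a dosed subject who dies of an MI on Day 40 with no other postdose record. SAP 5.6.2 means the adjudicated event to be in the treatment-emergent tables. But if an endpoint event is not an AE, it is unclear whether its report counts as a safety assessment for entry to the set. Under one reading the death is missing from the table of AEs leading to death; under the other it is there. A programmer would have to choose.

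The ITT set does not stand in for the missing denominator. It includes never-dosed subjects, and no exposure, compliance or AE table is planned on it. For those tables, no planned set is simply everyone who took the drug.

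**Working it through.** The documents give no figure for the size of the Safety Analysis Set, so there is nothing to reproduce. Two checks apply.

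**1. Which analyses are affected**

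| Analysis | Set | Postdose condition? |
|---|---|---|
| Time to MACE (SAP 5.4.1, 6.1.1) | Total Time (ITT) | No |
| Time to MACE+ (SAP 5.4.1) | Total Time (ITT) | No |
| MACE+ components, all-cause mortality (SAP 5.4.3) | Total Time (ITT) | No |
| Exposure, AEs, laboratory, vital signs, ECG (SAP 5.6) | Safety | Yes |
| Concomitant medication, compliance (SAP 5.2.6, 5.2.7) | Safety | Yes |

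**2. Upper bound on exclusions through drop-out**

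Inputs: 12,000 randomized, 5% annual drop-out and a 1.5% annual MACE rate (protocol 9.7.2; SAP 4); first postdose visit at Day 90 (SAP Table 8) with a window of plus or minus 10 days (protocol Table 4, footnote c).

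Assumptions: constant hazards, everyone randomized is dosed, and no early drop-out leaves any postdose safety record. The last makes the drop-out result an upper bound.

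Formula: N × (1 − exp(−rate × t)), with t in years.

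- Drop-outs by Day 90: 12,000 × (1 − exp(−0.05 × 90/365.25)) = 147, and 147/12,000 = 1.2%.
- Drop-outs by Day 100: 12,000 × (1 − exp(−0.05 × 100/365.25)) = 163, and 163/12,000 = 1.4%.

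Effect on an AE percentage if none of the 147 had the event: reported incidence = true incidence × 12,000/(12,000 − 147).

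- 5.00% becomes 5.06%.
- 20.0% becomes 20.2%.

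If all 147 fell in one arm of 6,000, a true 5.00% in that arm would show as 5.00% × 6,000/5,853 = 5.13%.

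**Early endpoint events.** The same formula at 1.5% a year gives 44 subjects with MACE by Day 90 and 49 by Day 100. Those with a nonfatal event stay in the study and normally supply later records. The ambiguity bites only for fatal events with nothing else on file, and the documents give no figure for that subset.

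**The case against.** The strongest reply is that Month 3 is only the first scheduled visit, not the first chance of a postdose record. Protocol 9.5.1.5 opens: "Safety assessments will consist of monitoring and recording all AEs and SAEs". AEs are collected continuously from consent, SAEs must be reported within 24 hours of awareness, and Table 4 has AE and endpoint reporting done by telephone when a visit is missed. A subject who stops because of poor tolerability will usually have a reported AE. One who stops drug permanently is due an end-of-treatment visit within about 30 days. A non-endpoint death is an SAE. All of this stands. It means the clause mainly removes subjects about whom nothing is known, and it is why the 1.2% to 1.4% is a ceiling.

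A reader might infer that early deaths fall out of every safety table. The documents do not support that. The primary safety analysis, each MACE+ component and all-cause mortality are run on all randomized subjects. A reader might also infer that an early fatal MI is excluded by rule. That goes too far: the event is entered on the AE form, reported expeditiously to the sponsor's safety department, and meant for the treatment-emergent tables, so the subject's membership is unsettled rather than denied. Finally, taking CV death as 25% to 50% of MACE (an assumption) gives 44 × 0.25 = 11 to 44 × 0.50 = 22 CV deaths by Day 90. Those are deaths expected to occur, not deaths excluded.

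The reply does not remove two facts: dosed subjects with no postdose record are dropped, and no rule says what counts as the qualifying assessment.

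**Conclusion.** The point holds as a small, avoidable defect in a denominator, together with an undefined membership rule. Exclusion through drop-out is at most about 147 to 163 of 12,000 (1.2% to 1.4%), assuming the planned drop-out rate applies evenly from randomization and no early drop-out has a postdose record. The true number cannot be found from the documents and is likely to be well below that. Overall AE percentages would move by a few hundredths to a few tenths of a percentage point. The more practical risk is that an individual early death appears in, or is absent from, the table of AEs leading to death according to how someone reads one undefined term. Alpha, power, and the 460 MACE and 1401 MACE+ event targets do not depend on this set.

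**What to change.** In all three places (protocol Synopsis, protocol 9.7.1.2 and SAP 5.2.1), define the Safety Analysis Set as all subjects who received at least one dose of study drug, and delete the postdose-assessment clause. Changing only some of them would leave the definitions in conflict. If the clause has to stay, the minimum is a sentence saying that any postdose AE, endpoint-event or vital-status record satisfies it.

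The cost is a wording change, made through the amendment or administrative-change route in protocol 11.1. No new data are collected, and denominators grow by no more than the 1.2% to 1.4% above. Laboratory percentages need no change, because SAP 5.6.3 already bases them on subjects with nonmissing baseline and postbaseline results. The programming specifications should say how compliance and exposure are shown for a subject with no returned tablets or no known last dose date.
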